8.2.3 EXPECTEDNESS

Expected adverse reactions are AEs that are common and known to occur for the study agent being studied. Expected adverse events of the treatment include transient tenderness, erythema, edema, and/or induration in the treated area lasting from one to three weeks after the treatment.

The device has a contact tissue cooling system in place during the procedure to minimize thermal discomfort and prevent damage to the treatment area. Expected adverse events related to the contact cooling include tingling, itching, decreased sensation, numbness, erythema and tenderness.

An AE or suspected adverse reaction is considered "unexpected" if it is not known to occur for the study treatment being studied and at the specificity or severity that has been observed.

8.3 TIME PERIOD AND FREQUENCY FOR EVENT ASSESSMENT AND FOLLOW-UP

The occurrence of an AE or SAE may come to the attention of study personnel during study visits and interviews of a study participant presenting for medical care, or upon review by a study monitor. All AEs

including local and systemic reactions not meeting the criteria for SAEs will be captured on the appropriate CRF. Information to be collected includes event description, time of onset, clinician's assessment of severity, relationship to study product (assessed only by those with the training and authority to make a diagnosis), and time of resolution/stabilization of the event. All AEs occurring while on study must be documented appropriately regardless of relationship. All AEs will be followed to adequate resolution.

Any medical condition that is present at the time that the participant is screened will be considered as baseline and not reported as an AE. However, if the study participant's condition deteriorates at any time during the study, it will be recorded as an AE. UPs will be recorded in the data collection system throughout the study.

Changes in the severity of an AE will be documented to allow an assessment of the duration of the event at each level of severity to be performed. AEs characterized as intermittent require documentation of onset and duration of each episode.

The PI will record all reportable events with start dates occurring any time after informed consent is obtained until 7 (for non-serious AEs) or 30 days (for SAEs) after the last day of study participation. At each study visit, the investigator will inquire about the occurrence of AE/SAEs since the last visit. Events will be followed for outcome information until resolution or stabilization.

8.4 REPORTING PROCEDURES

8.4.1 ADVERSE EVENT REPORTING

All AEs will be recorded on the appropriate CRF and will include information about the start and stop dates, severity and relatedness. There should be an attempt to report a "diagnosis" rather than the individual signs, symptoms and abnormal laboratory values associated with the diagnosis. However, a diagnosis should be reported only if, in the Investigator's judgment, it is relatively certain (i.e., definite or possible). Otherwise individual signs, symptoms and abnormal laboratory values should be reported as distinct adverse events.

8.4.2 SERIOUS ADVERSE EVENT REPORTING

All serious AE, whether or not deemed expected or device related, must be reported to the sponsor's clinical research department immediately or within 24 hours by telephone (see contact details below).

Name: [name], Clinical Research Manager

[contact] [name]

Email: [contact]

Address: [name]

A written report prepared by the Principal Investigator must follow within seven working days to the clinical monitor and should include a full description of the event and sequence.

The study investigator shall complete a Serious Adverse Event / Serious Adverse Device Effect Form and submit to the study sponsor and to the reviewing IRB as soon as possible, but in no event later than 10 working days after the investigator first learns of the effect. The study sponsor contact information is provided in Section 1, Key Roles. The study sponsor is responsible for conducting an evaluation of an

unanticipated adverse device effect and shall report the results of such evaluation to Health Canada, the FDA or local regulatory agency and to all reviewing IRBs and participating investigators within 10 working days after the sponsor first receives notice of the effect. Thereafter the sponsor shall submit such additional reports concerning the effect as Health Canada, the FDA or local regulatory agency requests.

8.4.3 UNANTICIPATED PROBLEM REPORTING

Incidents or events that meet the criteria for UPs require the creation and completion of an UP report form. It is the site investigator's responsibility to report UPs to their IRB and to the study sponsor. The UP report will include the following information:

Protocol identifying information: protocol title and number, PI's name, and the IRB project number;

- A detailed description of the event, incident, experience, or outcome;
- An explanation of the basis for determining that the event, incident, experience, or outcome represents an UP;
- A description of any changes to the protocol or other corrective actions that have been taken or are proposed in response to the UP.

An investigator shall submit to the sponsor and to the reviewing IRB a report of any unanticipated adverse device effect occurring during an investigation as soon as possible, but in no event later than 10 working days after the investigator first learns of the effect (21 CFR 812.150(a)(1)). A sponsor who conducts an evaluation of an unanticipated adverse device effect under 812.46(b) shall report the results of such evaluation to Health Canada, the FDA or local regulatory agency and to all reviewing IRB's and participating investigators within 10 working days after the sponsor first receives notice of the effect. Thereafter the sponsor shall submit such additional reports concerning the effect as FDA (21 CFR 812.150(b)(1)) or local regulatory agency requests.

8.4.4 REPORTING OF PREGNANCY

If a subject becomes pregnant during the course of the study, the subject will be terminated from the study. The pregnancy will be immediately reported to the sponsor on the Notification of Subject or Partner Pregnancy form and to the IRB using the same reporting timelines as a SAE. The investigator will follow the pregnancy until completion and will report the outcome of the pregnancy to the sponsor on the Notification of Subject or Partner Pregnancy Outcome form and the IRB within 10 business days.

8.5 STUDY HALTING RULES

The study may be halted at any time by the sponsor, the IRB, Health Canada, the FDA or local regulatory agencies due to safety concerns. Examples of findings that might trigger a safety review are the number of SAEs overall, the number of occurrences of a particular type of SAE, severe AEs/reactions, or increased frequency of events. If the study is halted, the sponsor will immediately notify all investigational sites, the IRB(s), Health Canada, the FDA or local regulatory agencies.

8.6 SAFETY OVERSIGHT

Independent oversight is an important component to ensure human subjects' protection. Safety oversight will be under the direction of the sponsor and a medical monitor.

9 CLINICAL MONITORING

Clinical site monitoring is conducted to ensure that the rights and well-being of human subjects are protected, that the reported trial data are accurate, complete, and verifiable, and that the conduct of the trial is in compliance with the currently approved protocol/amendment(s), with GCP, and with applicable regulatory requirement(s).

- Monitoring for this study will be performed by the sponsor or designate.
- On-site monitoring will occur within 10 weeks of first enrolled subject and will occur at a frequency described in the Monitoring Plan.
- Variables to be monitored will be described in the Monitoring Plan.
- The Study Director or designate will be provided copies of monitoring reports within 15 business days of visit.

10 STATISTICAL CONSIDERATIONS

10.1 STATISTICAL AND ANALYTICAL PLANS

The Statistical and Analytical Plans (SAP) may be revised during the study to accommodate Clinical Trial Protocol Amendments and to make changes to adapt to unexpected issues in study execution and data that affect planned analyses. If revised, a formal SAP will be completed and issued prior to database lock and unblinding of the study data.

10.2 STATISTICAL HYPOTHESES

The null and alternative hypotheses for the study's primary, key secondary and safety endpoints are;

- Primary Efficacy Endpoints: Statistical hypothesis will not be applied in the analysis of the study's primary endpoint
- Secondary Efficacy Endpoint(s):
 - Null Hypothesis ($H_0: \mu_d = \mu_{post} - \mu_{baseline} = 0$) – There is no change in thickness of the adipose layer as measured by ultrasound (US) at twelve weeks post-treatment as compared to baseline.

Alternative Hypothesis ($H_a: \mu_d = \mu_{post} - \mu_{baseline} \neq 0$) – There is a change in thickness of the adipose layer as measured by ultrasound (US) at twelve weeks post-treatment as compared to baseline. The efficacy endpoint to treatment will be defined by reduction in abdominal fat determined by decrease in thickness of the adipose layer as measured by ultrasound (US) at twelve weeks post-treatment as compared to baseline.

- Null Hypothesis ($H_0: \mu_d = \mu_{post} - \mu_{baseline} = 0$) – There is no change in abdominal circumference at twelve weeks post-treatment as compared to baseline.

Alternative Hypothesis ($H_a: \mu_d = \mu_{post} - \mu_{baseline} \neq 0$) – There is a change in abdominal circumference at twelve weeks post-treatment as compared to baseline. The change will

be defined by reduction in abdominal circumference at twelve weeks post-treatment as compared to baseline.

- Null Hypothesis ($H_0: \mu_d = \mu_{post} - \mu_{pre} = 0$) – There is no satisfaction with the treatment at twelve weeks using the 5-Point Likert Subject Satisfaction Scale as assessed by the subjects.

Alternative Hypothesis ($H_a: \mu_d = \mu_{post} - \mu_{pre} \neq 0$) – There is satisfaction with the treatment at twelve weeks using the 5-Point Likert Subject Satisfaction Scale as assessed by the subjects.

- Safety Endpoint: Statistical hypothesis will not be used in the analysis of the study's safety endpoint.

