10.4 DESCRIPTION OF STATISTICAL METHODS

10.4.1 GENERAL APPROACH

This is an open-label, baseline-controlled, evaluator-blind multi-center study evaluating one treatment with a 1060 nm diode laser for non-invasive fat reduction of the abdomen.

All summary tables for quantitative parameters will display mean, standard deviation, median, range (minimum and maximum), percentages as well as number of missing data (if relevant). All summary tables for qualitative parameters will display counts, percentages and number of missing data if relevant. Baseline data are defined as the last photograph and measurement performed before the first treatment on Visit 1.

All statistical tests will be two-sided, where applicable. The level of statistical significance for effectiveness analyses is 5% ($\alpha = 0.05$) for all tests of differences. Where appropriate, t-test and/or two-proportion z-test will be used to compare outcome at twelve weeks post-treatment as compared to baseline. This test will enable us to accept or reject the null hypotheses. Rejection of null hypotheses will establish that:

- The two-sided 95% confidence interval for the difference between the means excludes zero.
- The two means are statistically significantly different at the 5% level ($P < 0.05$) two-sided.

Upon rejection of null hypotheses, further statistical test tools such as Confidence Interval, and/or One-way ANOVA and/or descriptive statistical tools may be used to determine the performance of the treatment.

In order to accommodate imbalances of some baseline of scores or measurements, covariate adjustment analysis may be performed in SAP to estimate adjusted treatment effects for the primary endpoint analysis.

The assumption for the statistical test is that variables are normally distributed within study group and the variation of scores or measurements at twelve weeks post-treatment as compared to baseline is not reliably different.

The safety analysis will be done by analyzing spontaneous reports of adverse events (AE), subjects' completed 10 cm discomfort/pain visual pain scale and immediate response reports by the principal investigator from his/her observation/examination of the treated area. Appropriate Medical Dictionary for Regulatory Activities (MedDRA) code will be used to describe all spontaneously reported or other study related adverse events.

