10.4.3 ANALYSIS OF THE SECONDARY ENDPOINTS

For the analysis of changes in change in thickness of the adipose layer, abdominal circumference and subjects' assessment of satisfaction with the treatment secondary endpoints the following analysis will be considered:

Summary tables of changes in thickness of the adipose layer measured by ultrasound (US), abdominal circumference, and subjects' assessment of satisfaction at twelve weeks post-treatment as compared to baseline will be displayed as mean difference, standard deviation and standard error.

Bar charts, pie chart, graphs or any other descriptive statistical displays indicating scores, percentages and/or proportions of changes in thickness of the adipose layer measured by ultrasound (US), abdominal circumference, and subjects' assessment of satisfaction at twelve weeks post-treatment as compared to baseline will be used where applicable to analyse efficacy.

All statistical tests that will be two-sided. The level of statistical significance for effectiveness analyses is 5% ($\alpha = 0.05$) for all tests of differences. Where appropriate, two-proportion z-test will be used to compare the differences between of changes in thickness of the adipose layer measured by ultrasound (US), abdominal circumference, and subjects' assessment of satisfaction at twelve weeks post-treatment as compared to baseline. Analysis of Covariance (ANCOVA) may also be used where appropriate.

Change in thickness of the adipose layer measured by ultrasound (US), abdominal circumference, and subjects' assessment of satisfaction assessments at twelve weeks post-treatment as compared to baseline of all subjects who received at least one treatment of Venus Bliss™ and for whom at least one valid post-baseline assessment were obtained will be analysed for these secondary endpoints. Multiple imputation method or modelling of available data may be used for missing data as appropriate.

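### The satisfaction test has no pre-treatment score to use and no stated favourable direction, so once a reference is supplied a significant result on the dissatisfied side would carry the written conclusion of satisfaction

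*Combined protocol and SAP*

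**What the plan says.** Section 10.2 writes the satisfaction null as mu_post − mu_pre = 0 and words it "There is no satisfaction with the treatment at twelve weeks using the 5-Point Likert Subject Satisfaction Scale as assessed by the subjects". The alternative is mu_post − mu_pre ≠ 0, worded "There is satisfaction with the treatment at twelve weeks using the 5-Point Likert Subject Satisfaction Scale as assessed by the subjects". Nothing follows to say which sign counts as favourable.

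The other two tested secondary endpoints have the same two-sided form, but each has a direction sentence. For ultrasound: "The efficacy endpoint to treatment will be defined by reduction in abdominal fat determined by decrease in thickness of the adipose layer". For circumference, the change will "be defined by reduction in abdominal circumference at twelve weeks post-treatment as compared to baseline".

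Section 10.4.1 states "All statistical tests will be two-sided, where applicable", sets the level at 5%, and says "This test will enable us to accept or reject the null hypotheses". It ties rejection to a 95% confidence interval that excludes zero. Section 10.4.3 repeats two-sided testing, names satisfaction among the endpoints compared with baseline, offers a two-proportion z-test for it, and tabulates its mean difference.

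On timing, Section 7.3.4 has subjects complete the satisfaction scale at Visit 3 (Week 12), and the schedule of events marks that questionnaire at Week 12 only. The Visit 1 text (Section 7.3.2) lists the lifestyle questionnaire and the pain and response scales, but no satisfaction scale.

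**The concern.** The pair of hypotheses has two faults that should be repaired together.

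First, it is a post-minus-pre comparison of something measured once. Satisfaction with a treatment has no value before the treatment, and the plan does not collect one, so mu_pre is undefined.

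Second, the label and the formula do not match. The formula says different in either direction; the label says satisfied. For ultrasound and circumference the label is only that there is a change, and a further sentence then says which change counts. Satisfaction goes straight from a two-sided inequality to a favourable statement. Whoever repairs the first fault by inserting a reference value and leaves the rest alone will have a rule in which the sign of the result plays no part.

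Satisfaction is one of three endpoints with a formal hypothesis; Section 10.2 states none for the primary. A favourable statement should not be reachable from unfavourable answers.

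**Working it through.** **1. The three secondary hypotheses side by side (Section 10.2)**

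| Endpoint | Alternative | Wording of the alternative | Direction sentence | Baseline value collected |
|---|---|---|---|---|
| Ultrasound thickness | ≠ 0 | a change | yes, decrease | yes, Visit 1 |
| Circumference | ≠ 0 | a change | yes, reduction | yes, Visit 1 |
| Satisfaction | ≠ 0 | satisfaction | none | no, Week 12 only |

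Satisfaction is the only row with no direction sentence and no baseline, and the only one whose label is already favourable.

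**2. Inputs**

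- Two-sided α = 0.05 (Section 10.4.1). The sample size table in Section 10.5 prints the critical value 1.96. The normal quantile at 0.975 is 1.95996, so this reproduces, with 0.025 in each tail.
- n = 40 before dropout, 44 with dropout, up to 50 enrolled (Section 10.5). These were set on ultrasound; no sample size, effect or power is given for satisfaction.
- Assumptions, because the documents give no satisfaction mean, SD, reference or scale coding: a reference equal to the neutral category, a one-sample t-test, and a true mean δ standard deviations from neutral, with negative δ on the dissatisfied side.

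**3. Formula**

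T = (mean − reference) / (SD/√n) follows a noncentral t with n − 1 degrees of freedom and noncentrality δ√n. At n = 40 the critical value is 2.023. For δ = −0.5 the noncentrality is −0.5 × √40 = −3.16; for δ = −0.25 it is −1.58.

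**4. Probability that the null is rejected, so that the written conclusion is satisfaction**

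| True δ | n = 40 | n = 44 | n = 50 | n = 40, favourable direction also required |
|---|---|---|---|---|
| 0 | 0.050 | 0.050 | 0.050 | 0.025 |
| −0.25 | 0.338 | 0.368 | 0.410 | 0.0002 |
| −0.5 | 0.869 | 0.900 | 0.934 | below 0.000001 |
| −1.0 | about 1.00 | about 1.00 | about 1.00 | below 0.000001 |
| +0.5 | 0.869 | 0.900 | 0.934 | 0.869 |

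The last row shows that requiring the favourable direction costs no power on a mean score when subjects really are satisfied.

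**5. One worked data set**

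Assume codes 1 to 5 with 5 best, neutral 3, n = 40, observed mean 2.5, SD 1.0. The standard error is 1.0/√40 = 0.158. Then t = (2.5 − 3)/0.158 = −3.16 and two-sided p = 0.003. The 95% interval for the difference is −0.5 ± 2.023 × 0.158, that is −0.82 to −0.18. The interval excludes zero, the null is rejected, and the alternative as worded is satisfaction. The one-sided p for satisfaction is 0.998.

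**The case against.** Four things can be said for the plan.

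*The test cannot be run, so no wrong conclusion can be drawn from it.* This is right about the present text, and the missing pre-treatment score is the more basic fault. Section 7.1.1 does list patient-reported questionnaires at Visits 1 and 3, but it names no satisfaction scale at Visit 1. The direction fault appears only after a reference is supplied. It still stands as a separate item, because supplying a reference alone does not cure it.

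*Testing two-sided and reading direction from the estimate is ordinary practice.* It is, and Section 10.4.3 will display the mean difference, so the sign will be visible. Section 10.4.1 also allows confidence intervals and descriptive tools after rejection. Those steps are optional, and none makes the sign a condition for the conclusion. A careful analyst would not call a dissatisfied cohort satisfied, but the plan does not itself prevent it.

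*The probabilities come from assumed means and an assumed reference.* They do. They show how the rule behaves, not how likely dissatisfaction is.

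*The endpoint is secondary.* Success on the primary is tied to the 80% photographic criterion and the sample size to ultrasound, so the stakes are limited.

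A reader might also infer that, with codes 1 to 5, the test against zero must always reject because no mean can fall below 1. The documents do not support that. Zero is the null value of a difference, not a reference for the raw score, and no section gives the coding.

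**Conclusion.** The point holds in two parts. The satisfaction hypothesis cannot be tested as written, because it needs a pre-treatment score that is not collected. And it states no favourable direction, so after a reference is supplied a significant result on the dissatisfied side carries the same written conclusion as one on the satisfied side.

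Both parts follow from the text alone. The size rests on assumptions: with a neutral reference and a one-sample t-test, rejection in the wrong direction has probability about 0.34 to 0.41 at 0.25 SD, and 0.87 to 0.93 at 0.5 SD, for 40 to 50 subjects.

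It would go too far to say that the study will declare a dissatisfied cohort satisfied. The sign will be reported, and nothing in the documents suggests that subjects will be dissatisfied. What is missing is a decision rule that uses the sign. This is a moderate fault on a secondary endpoint and cheap to repair.

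**What to change.** In Section 10.2, replace the satisfaction pair with a one-sample directional rule on the Week 12 score:

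- State the coding of the five categories and which end is favourable.
- State the reference in advance. Two workable examples are the mean score against the neutral category, or the proportion in the two satisfied categories against a benchmark that the sponsor justifies (50% is only an example), with an exact interval.
- Conclude satisfaction only if the whole two-sided 95% confidence interval lies on the satisfied side of that reference. Report an interval wholly on the other side as dissatisfaction.
- If a proportion is used, say how subjects without a Week 12 answer are counted.

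In Section 10.4.3, take satisfaction out of the two-proportion z-test against baseline and out of the mean-difference tables, so that the two sections agree.

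The cost is wording in two sections, with no new data, subjects or visits; Section 10.1 already allows the analysis plan to be revised before database lock. A favourable claim becomes slightly harder to reach. Under the example benchmark of 50% with 40 answers, 27 satisfied subjects would be enough (exact lower limit 50.9%) and 26 would not (48.3%).

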10.3 ANALYSIS DATASETS

The Intention-to-Treat Analysis Dataset will be used; efficacy and safety analyses will be carried out on all subjects who underwent Venus Bliss™ treatment.

10.4 DESCRIPTION OF STATISTICAL METHODS

10.4.1 GENERAL APPROACH

This is an open-label, baseline-controlled, evaluator-blind multi-center study evaluating one treatment with a 1060 nm diode laser for non-invasive fat reduction of the abdomen.

All summary tables for quantitative parameters will display mean, standard deviation, median, range (minimum and maximum), percentages as well as number of missing data (if relevant). All summary tables for qualitative parameters will display counts, percentages and number of missing data if relevant. Baseline data are defined as the last photograph and measurement performed before the first treatment on Visit 1.

All statistical tests will be two-sided, where applicable. The level of statistical significance for effectiveness analyses is 5% ($\alpha = 0.05$) for all tests of differences. Where appropriate, t-test and/or two-proportion z-test will be used to compare outcome at twelve weeks post-treatment as compared to baseline. This test will enable us to accept or reject the null hypotheses. Rejection of null hypotheses will establish that:

- The two-sided 95% confidence interval for the difference between the means excludes zero.
- The two means are statistically significantly different at the 5% level ($P < 0.05$) two-sided.

Upon rejection of null hypotheses, further statistical test tools such as Confidence Interval, and/or One-way ANOVA and/or descriptive statistical tools may be used to determine the performance of the treatment.

In order to accommodate imbalances of some baseline of scores or measurements, covariate adjustment analysis may be performed in SAP to estimate adjusted treatment effects for the primary endpoint analysis.

The assumption for the statistical test is that variables are normally distributed within study group and the variation of scores or measurements at twelve weeks post-treatment as compared to baseline is not reliably different.

The safety analysis will be done by analyzing spontaneous reports of adverse events (AE), subjects' completed 10 cm discomfort/pain visual pain scale and immediate response reports by the principal investigator from his/her observation/examination of the treated area. Appropriate Medical Dictionary for Regulatory Activities (MedDRA) code will be used to describe all spontaneously reported or other study related adverse events.

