10.5 SAMPLE SIZE

The change in thickness of the adipose layer as measured by ultrasound (US) at twelve weeks post-treatment as compared to baseline secondary endpoint outcome measures was used to calculate the study sample size.

Sample size calculation using secondary endpoint outcome measure;

- Null and alternate hypotheses:

Null Hypothesis ($H_0: \mu_d = \mu_{post} - \mu_{baseline} = 0$) – There is no change in thickness of the adipose layer as measured by ultrasound (US) at twelve weeks post-treatment as compared to baseline.

Alternative Hypothesis ($H_a: \mu_d = \mu_{post} - \mu_{baseline} \neq 0$) – There is a change in thickness of the adipose layer as measured by ultrasound (US) at twelve weeks post-treatment as compared to baseline. The efficacy endpoint to treatment will be defined by reduction in abdominal fat determined by decrease in thickness of the adipose layer as measured by ultrasound (US) at twelve weeks post-treatment as compared to baseline.

Expected reduction in abdominal fat of 2.65 + 1.41 obtained from a similar study (,Bass LS et al) will be used to determine the sample size.

- In view of the nature of this study in regard to number of visits, we make provision for 10% study drop out, withdrawal or loss to follow-up.
- 2-Tailed Sample Size calculation formula for two Samples was used in the table below:

(1- β), Desired Power	0.8
α , Level of Significance	0.05
μ_d , expected reduction in abdominal fat measured from baseline to 3 month post treatment visit under H_a	2.65
σ , Standard Deviation (obtained from a study)	1.41
$Z_{1-\alpha/2}$	1.96
$Z_{1-\beta}$, (for 80%)	0.84
Estimated Sample Size	40
Estimated Sample Size of each equal group + 10% drop out	44

Conclusion: The estimated sample size for the study and the additional 10% provision for drop out (**44 subjects**) obtained from the secondary endpoint outcome measure calculation is required for this study. However, to ensure statistical significance, up to 50 subjects will be enrolled.

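### Section 10.4.1 allows a non-significant ultrasound or circumference result to be accepted as no change, and mentions confidence intervals only in connection with rejection

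*Combined protocol and SAP*

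**What the plan says.** Section 10.4.1 (General Approach) names the tests: "Where appropriate, t-test and/or two-proportion z-test will be used to compare outcome at twelve weeks post-treatment as compared to baseline". It then gives the decision rule: "This test will enable us to accept or reject the null hypotheses".

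Two statements about confidence intervals follow. The first says that rejection establishes a two-sided 95% interval excluding zero. The second reads: "Upon rejection of null hypotheses, further statistical test tools such as Confidence Interval, and/or One-way ANOVA and/or descriptive statistical tools may be used". Nothing in the section says how a result that is not rejected should be described or displayed.

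Section 10.2 (Statistical Hypotheses) supplies the statement that would be accepted. For circumference it is: "There is no change in abdominal circumference at twelve weeks post-treatment as compared to baseline". The ultrasound null has the same form. No test applies to the primary photograph endpoint.

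Section 10.4.3 (Analysis of the Secondary Endpoints) requires summary tables of change that "will be displayed as mean difference, standard deviation and standard error". These do not depend on the test result, and they contain no confidence interval.

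Section 10.5 (Sample Size) sizes the trial on ultrasound thickness: for that measure, the "secondary endpoint outcome measures was used to calculate the study sample size".

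**The concern.** A test of zero difference gives evidence against zero or fails to give it. It cannot establish that the change is zero unless a margin of negligible change is set and the interval is shown to lie inside it. The documents set no such margin. If *accept* is taken literally, P ≥ 0.05 leads to the conclusion in 10.2 that there was no change, and no other section corrects that reading.

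The interval is the tool that would prevent the mistake, because it shows which reductions remain compatible with the data. It is needed most when the test is not significant, yet the plan mentions it only when the test is significant.

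What is at stake is the wording of a secondary result. Ultrasound and circumference are the continuous endpoints that the plan tests, so this rule governs the formal inference on both. Circumference is the more exposed, because nothing in the documents says how precisely its change will be estimated.

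**Working it through.** **Inputs from the documents**
- Significance level (10.4.1): "The level of statistical significance for effectiveness analyses is 5% ($\alpha = 0.05$) for all tests of differences".
- Sidedness (10.4.1): "All statistical tests will be two-sided, where applicable".
- Number of completers (10.5): 40 before the dropout allowance, and at most 50 enrolled.
- Ultrasound (10.5): expected reduction 2.65, SD 1.41.
- Circumference: no expected effect, SD or power is given.

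**The plan's own figure.** The documents state no number for circumference that could be reproduced. The stated 40 is for ultrasound and does not follow from its inputs. The two-sample formula gives 2 × (1.96 + 0.84)² × 1.41² / 2.65² = 4.44, so 5 per group. That is a separate matter, and 40 is used below only as the plan's target number of completers.

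**Assumptions.** A paired t-test on within-subject change (10.4.1 says only t-test); an SD of circumference change of 2, 3 or 4 cm; a true reduction of 1 cm, with 2 cm as a second case. None of these is in the documents.

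**Step 1: precision.** Half-width of the 95% interval = t(0.975, n−1) × SD / √n. This is 0.320 × SD at n = 40 and 0.284 × SD at n = 50.

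**Step 2: chance of a non-significant result when the change is real.** This is the type II error from the noncentral t distribution, with noncentrality = true change × √n / SD.

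| Assumed SD (cm) | Half-width, n = 40 (cm) | Half-width, n = 50 (cm) | Type II error, 1 cm, n = 40 | Type II error, 1 cm, n = 50 | Type II error, 2 cm, n = 40 |
|---|---|---|---|---|---|
| 2 | 0.64 | 0.57 | 13% | 7% | about 0% |
| 3 | 0.96 | 0.85 | 46% | 36% | 2% |
| 4 | 1.28 | 1.14 | 66% | 59% | 13% |

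The n = 50 columns assume that all 50 subjects complete. At n = 40 the change detectable with 80% power is 0.454 × SD, which is 1.36 cm at an SD of 3 cm.

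**Step 3: an illustrative result (assumed data).** Take n = 40, mean change −0.8 cm and SD 3 cm.
- SE = 3 / √40 = 0.47 cm.
- t = −0.8 / 0.474 = −1.69, so P = 0.10.
- 95% interval = −0.8 ± 0.96 = −1.76 to +0.16 cm.

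Read literally, 10.4.1 has this accepted as no change and calls for no interval. The interval includes zero, but also a reduction of about 1.8 cm. The correct statement is that a change was not demonstrated.

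**Step 4: ultrasound, for contrast.** If the stated 2.65 and 1.41 hold, an exact paired t-test passes 80% power with 5 subjects. A non-significant result is then unlikely, and the wording matters less in practice.

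**The case against.** The strongest reply is that *accept or reject* is common loose phrasing and that the plan draws no conclusion from acceptance. Section 10.4.1 lists what rejection establishes and is silent on the other outcome. That stands in part. A reader might infer that the plan commits the sponsor to report a non-significant circumference result as evidence of no change. No section says so. The supported claim is that 10.4.1 and 10.2 together allow that conclusion and nothing rules it out.

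A reader might also infer that intervals are barred after a non-significant test. They are not. The sentence is permissive, and it lists descriptive tools beside the interval, although 10.4.3 provides descriptive tables without condition. Those tables give the mean difference and SE, and 10.4.11 lists individual data, so an interval can be derived. It is still not planned, and deriving it would not correct the decision wording.

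The percentages could be mistaken for the harm done by the wording. They are hypothetical type II error rates under an assumed effect and assumed SDs, and rewording the rule leaves each unchanged. They show only that a non-significant result is plausible enough to need a correct reading. The documents do not show that circumference will be imprecise.

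Finally, a reader might conclude that one-way ANOVA has no use in a single-group study and should be deleted. That goes too far. There are up to 5 sites (5.3), and 10.4.9 allows analysis by demographic characteristics, so comparing change scores across such groups is a real question. The fair remark is that 10.4.1 names no factor.

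**Conclusion.** The concern holds as a minor defect in the decision wording and in what is reported. Sections 10.4.1 and 10.2, read literally, let P ≥ 0.05 be concluded as no change in ultrasound thickness or circumference, and no interval is planned to show otherwise. This rests on the text alone and needs no assumed figure. The likelihood of meeting the problem does rest on assumptions: it is small if the SD of circumference change is about 2 cm or the true reduction about 2 cm, and considerable if the SD is 3 to 4 cm and the true reduction 1 cm.

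The study's success decision is unaffected, because the primary criterion in 10.4.2 is an average of 80% correct identification without a hypothesis test.

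**What to change.** In 10.4.1:
- Replace the accept-or-reject wording with *reject or fail to reject*.
- Add that P ≥ 0.05 means a change was not demonstrated, and that it is not evidence of no change.
- Remove the condition that ties the confidence interval to rejection.

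In 10.4.3, report the mean within-subject change with its two-sided 95% confidence interval for ultrasound thickness and for circumference, whatever the P value. Satisfaction is left out because the schedule of events collects it only at week 12, so there is no within-subject change to put an interval on.

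The cost is a few sentences and one more column in a planned table. Sample size, alpha, visits and data collection stay as they are. Section 10.1 already provides for a revised SAP issued before database lock. There is no downside.
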